8.5.4.3 Expectedness

The Investigator will be responsible for determining whether an SAE is expected or unexpected. An SAE will be considered unexpected if the nature, severity, or frequency of the event is not consistent with the risk information previously described for the investigational product.

8.5.5 Time Period and Frequency for Event Assessment and Follow-up

All AEs will be collected from the signing of the ICF until the End-of-Study Follow-up visit.

Whenever possible, all AEs should be followed until satisfactory resolution or until the site Investigator deems the event to be chronic or the patient is stable.

All SAEs will be recorded and reported to the sponsor or designee within 24 hours, whether considered investigational product related or not, and must include an assessment of if there is a reasonable possibility that the investigational product caused the event. The Investigator will also submit any updated SAE data to the sponsor within 24 hours of it being available.

Investigators are not obligated to actively seek AEs or SAEs after conclusion of the study participation. However, if the Investigator learns of any SAE, including a death, at any time after a patient has been discharged from the study, and he or she considers the event to be reasonably related to the investigational product or study participation, the Investigator must promptly notify the sponsor.

8.5.6 Adverse Event Reporting

At each study visit, patients will be evaluated for new AEs and the status of existing AEs. Care will be taken not to introduce bias when evaluating for AEs. The Investigator should use open-ended questions when soliciting information from a patient regarding AEs, followed by appropriate questions that clarify the patient's verbatim description of AEs or change in concomitant medications.

When an AE occurs, it is the responsibility of the Investigator to review all documentation (e.g., hospital progress notes, laboratory reports, and diagnostics reports) related to the event. The Investigator will attempt to establish a diagnosis of the event based on signs, symptoms, and/or other clinical information. Whenever possible, the diagnosis (not the individual signs/symptoms) will be documented as the AE.

The Investigator will then record all relevant AE information in the CRF. It is not acceptable for the Investigator to send photocopies of the patient's medical records in lieu of completion of the CRF page. New or updated information will be recorded in the originally completed CRF. However, there may be instances when copies of medical records for certain cases are requested. In this case, all patient identifiers, with the exception of the patient number, will be redacted on the copies of the medical records before submission.

If a patient dies during participation in the study or during a recognized follow-up period, the Investigator will provide a copy of any postmortem findings, including histopathology when available.

If a site receives report of a new SAE from a study patient or receives updated data on a previously reported SAE after database lock of the electronic data capture (EDC) system, then the site can report this information on a paper SAE form or to the sponsor by telephone. See the Study Manual for additional information on SAE reporting.

The study sponsor, or designee, will be responsible for notifying all applicable regulatory authorities of any required safety events in compliance with country-specific regulatory requirements. In addition, the sponsor must notify applicable regulatory authorities and all participating Investigators of suspected unexpected serious adverse reactions (SUSARs), from clinical trials or any other source.

An Investigator who receives an Investigator safety report describing a SAE or other specific safety information (e.g., summary or listing of SAEs) from the sponsor will review and then file it along with the IB and will notify the Institutional Review Board/Independent Ethics Committee (IRB/IEC), if appropriate according to local requirements.

8.5.7 Reporting of Pregnancy

Pregnancy itself is not regarded as an AE unless there is a suspicion that the investigational product may have interfered with the effectiveness of a contraceptive medication. Pregnancy in a patient's partner is not considered an AE. Abnormal pregnancy outcomes (e.g., spontaneous abortion, fetal death, stillbirth, congenital anomalies, ectopic pregnancy) are considered SAEs. Elective abortions without complications should not be handled as AEs; however, an induced therapeutic abortion to terminate a pregnancy because of complications or medical reasons must be reported as an SAE. The underlying medical diagnosis for this procedure should be reported as the SAE term. A spontaneous abortion in a study patient is always considered an SAE.

All pregnancies in female patients and, if indicated, pregnancies in female partners of male patients, will be collected after the start of investigational product and until 5 weeks after the last dose. Pregnancy outcomes, defined as the first well baby visit for live births, or spontaneous or induced abortion, will be documented even after the patient is withdrawn from or completes the study.

If a pregnancy is reported, the Investigator should inform the sponsor within 24 hours of learning of the pregnancy and should follow the procedures outlined in [Appendix 2](#).

8.6 Treatment of Overdose

There are no data on overdose because this is the first study of BOS-589 in patients and, in a prior study in healthy human volunteers, no evidence of overdose was reported. There is no definition of what constitutes an overdose and no known antidote. Any patient who receives a higher dose than that intended (i.e., more than 200 mg per dose; more than 400 mg in a given day) should be monitored closely, managed with appropriate supportive care, and followed up appropriately. If possible, a blood sample for PK should be collected as soon as is feasible from any patient who takes a higher dose than that intended.

If AEs or SAEs are reported and are considered related to a patient receiving a higher dose than intended, dosing should be interrupted if deemed necessary by the Investigator and the case discussed further with the Medical Monitor.

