6.3 Measures to Minimize Bias

This is a randomized, double-blinded, PBO-controlled study. Patients should be randomized as close as possible to the time of the planned first dose of study treatment.

Randomization will be conducted via an interactive web response system (IWRS) in a 1:1:1 ratio for patients to receive BOS-589 200 mg, BOS-589 50 mg, or PBO. Patients will be assigned to the treatment arms using a permuted block randomization stratified by site (44 patients per group). The randomization schedule will be generated by the Study Biostatistician and will be transferred to the IWRS team for loading into the system. The randomization file will be held by the Study Biostatistician until the end of the trial and when the database has been locked.

The sponsor, site staff, and patients will be blinded to the treatment assignment. BOS-589 and PBO will be similar in appearance, and provided in white, opaque, high-density polyethylene (HDPE) bottles, each with a child-resistant closure. Each bottle will be labeled as per country requirement.

Only in a medical emergency will a patient's treatment assignment be unblinded, and this process will be performed and documented in the IWRS. Every effort should be made to contact the Medical Monitor to discuss unblinding prior to breaking the blind.

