6.5 Dose modification

Study treatment should be interrupted if the patient reports any treatment-related severe AE. Therapy should only be restarted after approval by the Medical Monitor.

If therapy is restarted, the same dose should be administered as that prior to occurrence of the AE. If the patient is still having tolerability issues and an AE reoccurs, the dose may be reduced from 2 tablets of study treatment bid to 1 tablet of study treatment bid, without breaking the study blind.

If another AE occurs after the study treatment dose reduction, study treatment will be permanently discontinued and the subject followed until the end of the study.

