7.2 Discontinuation/Withdrawal from the Study

A patient may withdraw from the study at any time at his or her own request or may be withdrawn at any time at the discretion of the Investigator for the following reasons:

- If any clinical AE, laboratory abnormality, or other medical condition or situation occurs such that continued participation in the study would not be in the best interest of the patient;
- Disease progression that requires discontinuation of the investigational product;
- Pregnancy;
- If the patient meets an exclusion criterion (either newly developed or not previously recognized) that precludes further study participation after consultation with the Medical Monitor;
- Significant investigational product noncompliance;
- Termination of the study by the sponsor.

If the patient withdraws consent for disclosure of future information, the sponsor may retain and continue to use any data collected before such a withdrawal of consent.

If a patient withdraws from the study, he or she may request destruction of any samples taken and not tested, and the Investigator must document this in the site study records.

See Schedule of Activities, Section 1.3, for data to be collected at the time of study discontinuation and follow-up and for any further evaluations that need to be completed.

The reason for patient discontinuation or withdrawal from the study will be recorded on the CRF.

Patients who sign the ICF and are randomized but do not receive the investigational product may be replaced. Once randomized, patients who are withdrawn from therapy before completing 28 days of dosing or are discontinued from the study for any reason will not be replaced.

Clinical and/or laboratory criteria that may warrant study drug discontinuation.

If a patient experiences any of the following clinical or laboratory events, study treatment should be immediately suspended:

- Any SAE considered study drug-related;
- No bowel movement for 4 days;
- Any clinical evidence suggestive severe constipation, obstipation or intestinal obstruction; gastrointestinal hemorrhage, significant gastrointestinal infection;
- Abnormal liver functions concerning for drug-induced as follows¹:
 - Confirmed ALT > 5x ULN
 - Confirmed ALT > 3x ULN and any of the following signs or symptoms (fatigue, nausea, vomiting, right upper quadrant pain, fever, rash or eosinophilia)²
 - Confirmed ALT > 3x ULN and total bilirubin > 2x ULN or INR > 1.5 (**should be repeated in 48-72 hours**)

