¹Should any of these events occur, a full evaluation of other causes of liver enzyme elevation should be undertaken and patients would be followed at regular intervals until labs return to normal/stabilize, or an alternate diagnosis is confirmed.

²If patients develop asymptomatic elevations of the ALT of > 3x ULN and, if there are persistent elevations upon repeat testing, close observation should be implemented, and discontinuation of the drug should be considered.

Depending on the nature, severity, and outcome, the Sponsor will decide to (and document with supporting rationale) either: 1) discontinue study drug; 2) request additional safety data; or 3) continue dosing at current dose or reduced dose (see [Section 6.5](#)).

If 2 or more patients experience any of the above criteria (note: study drug-related SAEs must be in the same system organ class) the study enrollment will be halted. The Sponsor, an independent GI physician not involved with the study, and the lead

investigator will review available data to determine whether individual patient unblinding is warranted, amendments are required for the protocol, and whether patients currently on treatment should also discontinue study drug. A decision to continue (with or without modifications) or discontinue the study will be made. All supporting rationale will be documented.

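### Minor: the close-monitoring trigger in Protocol 8.6 is fixed at the Cohort 1 full dose in mg, so a patient reduced to 1 tablet bid who takes 2 is not flagged

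*Protocol*

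**What the plan says.** Protocol 8.6 (Treatment of Overdose) states that overdose has no definition in this study. It then asks for close monitoring, supportive care and follow-up of any patient who receives "a higher dose than that intended (i.e., more than 200 mg per dose; more than 400 mg in a given day", where the bracket ends. The next sentence asks, if possible, for a PK sample "from any patient who takes a higher dose than that intended". The second paragraph says that where AEs or SAEs "are considered related to a patient receiving a higher dose than intended, dosing should be interrupted if deemed necessary by the Investigator", and that the case then goes to the Medical Monitor.

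Four other sections bear on this:

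- **6.4** sets the full dose at 2 tablets twice daily in every cohort: 100 mg tablets in Cohort 1, 25 mg tablets in Cohort 2 and placebo tablets in Cohort 3.
- **6.3** says: "The sponsor, site staff, and patients will be blinded to the treatment assignment".
- **6.5** provides that, if an AE recurs after treatment has been interrupted and restarted, "the dose may be reduced from 2 tablets of study treatment bid to 1 tablet of study treatment bid, without breaking the study blind". It adds: "If another AE occurs after the study treatment dose reduction, study treatment will be permanently discontinued".
- **7.2** lists events after which "study treatment should be immediately suspended". One of the sponsor's options afterwards is to "continue dosing at current dose or reduced dose", with a cross-reference to 6.5.

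**The concern.** The trigger is worded relative to what was intended for the patient, but the bracket gives that phrase one absolute meaning for everyone. The protocol creates more than one intended dose: two active full doses, placebo, half of each after a reduction, and none during an interruption or suspension. The bracket matches only the largest.

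The reduced patient is the case that matters. Under 6.5 that patient has had a treatment-related severe AE, restarted, and had an AE recur at 2 tablets bid. Under 7.2 the patient has had a suspension event, such as a drug-related SAE, 4 days without a bowel movement, or confirmed ALT above 5 times ULN. Going back to 2 tablets by mistake returns the patient to the dose at which the problem arose. At stake is whether that error prompts close monitoring and follow-up.

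**Working it through.** **Inputs.** Limits from 8.6: more than 200 mg per dose, more than 400 mg per day. Tablet strengths from 6.4: 100 mg (Cohort 1), 25 mg (Cohort 2), 0 mg (placebo). Full dose from 6.4: 2 tablets bid. Reduced dose from 6.5: 1 tablet bid.

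**1. Reproduce the bracket.** Cohort 1 full dose: 2 x 100 = 200 mg per dose, and 2 x 200 = 400 mg per day. These equal the two limits exactly.

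**2. Convert to tablets.** 200/100 = 2 per dose and 400/100 = 4 per day. Exceeding either means at least 3 per dose or at least 5 per day. This conversion is not in the protocol. It is the most favourable reading a blinded site could use, and it works for every full-dose patient, because the full tablet count is the same in all three cohorts.

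**3. Apply it to a reduced patient** (prescribed 1 per dose, 2 per day).

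| Tablets taken in the day | Largest dose | Day total | Over 2 per dose or 4 per day? | Cohort 1 mg: dose, day | Over 200 or 400 mg? |
|---|---|---|---|---|---|
| 2 then 1 | 2 | 3 | No | 200, 300 | No |
| 2 then 2 | 2 | 4 | No | 200, 400 | No |
| 3 then 1 | 3 | 4 | Yes | 300, 400 | Yes |

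In the second row the intake is 2/1 = 4/2 = 2 times the prescribed dose. It is not flagged on the tablet reading or on the mg reading. In Cohort 2 the same row is 2 x 25 = 50 mg per dose and 4 x 25 = 100 mg per day, also below both limits.

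**4. Apply it to an interrupted or suspended patient.** The intended dose is zero. Taking 2 tablets bid again gives 2 per dose and 4 per day, and neither limit is exceeded.

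**5. The limits taken literally in mg.** In Cohort 2, 200/25 = 8 and 400/25 = 16, so flagging would start at 9 tablets per dose or 17 per day. A placebo patient could never be flagged. A site would have to know the allocation to apply this reading, so the point does not rest on it.

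**The case against.** The best defence is that the bracket marks the highest dose the trial assigns, and that this is a reasonable anchor for overdose handling. A reduced patient who takes 2 tablets is back on the randomized dose, which patients in that cohort take for 28 days without extra monitoring. Section 2.2.3.2 reports single doses up to 400 mg and 200 mg bid for 14 days as generally safe and well tolerated in healthy volunteers. Section 6.6 requires tablet counts and recording of dosing deviations. Visits are weekly with AE review, and any further AE after a reduction ends treatment for good. The scenario needs several events in 4 weeks, and a site that converts mg to tablets might also see that 2 is too many for this patient.

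Much of this stands, and it is why the point is minor. It does not rescue the wording. Healthy-volunteer tolerability says little about a patient who has already had an event at that dose. Recording a deviation does not start close monitoring, and the stopping rule acts only after another AE. A site that looks past the bracket to the prescribed dose is correcting the protocol, not following it.

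Two stronger readings are tempting:

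- A reader might infer that 8.6 contradicts itself, because the PK sentence and the second paragraph use the phrase without the bracket. The text does not establish that. Once explained, a phrase can carry the same meaning a sentence or two later.
- A reader might infer that the present bracket also flags compliant patients who take a dose late. Assume doses at 09:00 and 21:00, with one evening dose taken at 00:30. That is 3.5 hours late and allowed by 6.4, and the calendar day then holds 3 x 200 = 600 mg in Cohort 1. The result depends on the assumed schedule and on counting by calendar day and not by scheduled doses. Section 8.6 does not say which is meant.

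**Conclusion.** The point holds as a minor error of wording. On its stated terms the 8.6 trigger gives the wrong answer for a reduced patient who takes up to twice the prescribed dose, whether the limits are read in mg or in tablets. The arithmetic is certain. How often this would matter is unknown, because the documents give no expected number of reductions. Whether sites would in practice overlook such a patient is a matter of judgement.

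A reader might infer exposure above the studied range, or harm to the trial's results. The documents support neither. The unflagged intake never exceeds the full randomized dose, and no endpoint, analysis set or test in the SAP uses the 8.6 trigger.

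**What to change.** Replace the bracket in 8.6 with: *(i.e., more tablets than currently prescribed for that patient, in any cohort; for example, more than 2 per dose or more than 4 per day at full dose, more than 1 per dose or more than 2 per day after a reduction, or any tablet while dosing is interrupted or suspended)*. This needs no knowledge of the allocation. Making the limits examples of a general rule keeps a patient whose intended dose is zero within it.

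Optionally, add that a dose taken late within the four-hour rule of 6.4 is not excess. This matters if a day is counted by the calendar. On the schedule assumed above, a compliant patient would reach 3 x 2 = 6 tablets at full dose, or 3 x 1 = 3 after a reduction.

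The cost is one bracket, the optional sentence and a matching CRF instruction. The downside is that a few extra placebo or low-dose patients are monitored and sampled.

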8.7 Pharmacokinetics

Plasma samples of approximately 4 mL will be collected for measurement of plasma concentrations of BOS-589 at the following times and as specified in the Schedule of Activities ([Section 1.3](#)).

- On Day 1 at predose and at 0.5, 1, 2, and 4 hours postdose.

- On Day 15 at predose and at 0.5, 1, 2, and 4 hours postdose. If samples cannot be obtained on Day 15, then samples should be obtained on Day 22.
- A predose sample will be obtained on all other Treatment Study Visits.

Allowable sampling windows for PK blood draws will be 30 minutes prior to dosing for the predose sample, then \pm 5 minutes for the 0.5 and 1 hour postdose timepoints, and \pm 10 minutes for the 2 and 4 hours postdose timepoints.

Instructions for the collection and handling of biological samples will be provided by the sponsor. The actual time of dosing and actual date and time (24-hour clock time) of each sample will be recorded.

Drug concentration information that may unblind the study will not be reported to investigative sites or blinded personnel until the study has been unblinded.

Any changes in the timing or addition of timepoints for any planned study assessments must be documented and approved by the relevant study team member and then archived in the sponsor and site study files but will not constitute a protocol amendment. The IRB/IEC will be informed of any safety issues that require alteration of the safety monitoring scheme or amendment of the ICF.

The following PK parameters will be estimated from the plasma concentrations of BOS-589 using either traditional noncompartmental methods or a population-PK model:

AUC_{0-t}	Area under the plasma concentration versus time curve from time zero to the last quantifiable sample;
AUC_{0-4}	Area under the plasma concentration versus time curve from time zero to 4 hours postdose;
C_{max}	Maximum observed plasma concentration;
C_{min}	Minimum observed plasma concentration.
T_{max}	time to maximum concentration

In addition to parameters above, the AUC from time zero to 4 hours postdose (AUC_{0-12}) may be calculated using predose concentrations other than Day 1 predose to impute a 12-hour concentration. Details will be provided in the PK analysis plan.

8.8 Biomarkers/Pharmacodynamics

CCI

CCI

9 STATISTICAL CONSIDERATIONS

9.1 Timing of Analyses

Formal hypothesis testing will occur at the end of the study and post database lock. There are no planned Data, Safety, or Adjudication Committees for this study and no planned statistical interim analyses.

9.2 Sample Size Determination

This is a phase 2a study in which a hierarchical hypothesis test will be employed for the primary efficacy endpoint. The primary endpoint is defined as a change in the 24-hour WAP score at Day 29 compared to baseline (averaged over the week prior to each respective timepoint). Mean change from baseline will be measured as a continuous variable and compared between treatment groups in a hierarchical testing order using a t-test of equal variances and a two-tailed alpha of 0.05.

The sample size was based on the first hypothesis test in the hierarchical plan, with 80% power, two-sided alpha of 0.05, and a standard deviation (SD) of 3 points on the NRS to detect a 1.6 minimum change between treatment groups (N = 120 patients). To account for attrition and a potential higher PBO rate, a total of 132 patients will be randomized to one of 3 treatment groups in a 1:1:1 ratio (44 patients per treatment group).

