9.4.1 Efficacy Analyses

9.4.1.1 Primary Endpoint

This is a proof-of-principle study in which a hierarchical hypothesis test will be employed for the primary efficacy endpoint, defined as a change in the 24-hour WAP score at Day 29 compared to baseline (averaged over the week prior to each respective timepoint). Mean change from baseline will be measured as a continuous variable and compared between treatment groups in the following testing order using a t-test of equal variances and a two-tailed alpha of 0.05:

Hypothesis 1:

Active Treatment Group (Cohort 1 + Cohort 2) versus PBO (Cohort 3);

If statistically significant at $P < 0.05$, then proceed to Hypothesis 2.

Hypothesis 2:

Cohort 1 (High Dose) versus Cohort 3 (PBO);

If statistically significant at $P < 0.05$, then proceed to Hypothesis 3.

Hypothesis 3:

Cohort 2 (Low Dose) versus Cohort 3 (PBO);

If statistically significant at $P < 0.05$ then, proceed to Hypothesis 4.

Hypothesis 4:

Cohort 1 (High Dose) versus Cohort 2 (Low Dose).

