3.4. Sample Size Considerations

This is a phase 2a study in which a hierarchical hypothesis test will be employed for the primary efficacy endpoint. The primary endpoint is defined as a change in the 24-hour WAP score at Day 29 compared to baseline (averaged over the week prior to each respective timepoint). Mean change from baseline will be measured as a continuous variable and compared between cohorts in a hierarchical testing order using a t-test of equal variances and a two-tailed alpha of 0.05.

Sponsor: Boston Pharmaceuticals, Inc.
Protocol Number: BOS-589-201
Version and Date: Version 1.2 12NOV2020

The sample size was based on the first hypothesis test in the hierarchical plan, with approximately 80% power, two-sided alpha of 0.05, and a standard deviation (SD) of 3 points on the numeric rating scale to detect a 1.6 minimum change between cohorts (N = 120 patients). To account for attrition and a potential higher Placebo rate, a total of 132 patients will be randomized to one of 3 cohorts in a 1:1:1 ratio (44 patients per cohort).

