5.8. Lost to Follow Up or Lapse of Adequate Assessments

A patient will be considered lost to follow-up if he or she repeatedly fails to return for scheduled visits and is unable to be contacted by the study site staff. Missing evaluations will not be imputed.

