7. EFFICACY

Efficacy analyses will be conducted using the ITT and PP Analysis Sets.

All available efficacy data will be provided in by-patient data listings on all ITT patients.

The efficacy objectives of the study are to evaluate the effect of BOS-589, relative to Placebo after 4 weeks of therapy, on pain, defecation, and key IBS-D related signs and symptoms.

During the 4 weeks of the double-blind treatment phase, patients will be required to access their electronic diary every day, preferably at the same time each day, to record IBS-D symptom data and information related to their bowel function and rescue medication use.

For all efficacy endpoints, the Day 29 visit change from baseline is the main timepoint of interest. However, unless stated otherwise, data will be presented for each planned visit (Baseline/Day 1, Day 8, Day 15, Day 22, Day 29, and Day 43).

For efficacy endpoints collected daily, the baseline score will be the average of non-missing scores reported for the last 7 days prior to the date where eligibility and run-in criteria pertaining to IBS-D symptom and bowel function have been met. The Day 29 visit score will be the average of non-missing scores reported during the 7 days prior to the Day 29 visit. The Day 8 visit, Day 15 visit, Day 22 visit, and Day 43 visit scores are calculated in a similar manner. If there are missing daily scores on any day, the visit score will be averaged from all the non-missing values during the 7 days prior to the visit. No imputation of the missing values will be made. For the Day 29 calculation only, a window of ± 14 days relative to actual calculated day 29 from dosing will be applied such that any Day 29 visit occurring outside that window will be excluded.

Sponsor: Boston Pharmaceuticals, Inc.
Protocol Number: BOS-589-201
Version and Date: Version 1.2 12NOV2020

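### Does the protocol's 80% power at N = 120 need correcting, given that its printed inputs give about 78%?

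*Protocol*

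**What the plan says.** Protocol 9.2 ties the sample size to Hypothesis 1: "The sample size was based on the first hypothesis test in the hierarchical plan, with 80% power", at two-sided alpha 0.05, with "a standard deviation (SD) of 3 points on the NRS to detect a 1.6 minimum change between treatment groups (N = 120 patients"). Protocol 9.4.1.1 defines that hypothesis as "Active Treatment Group (Cohort 1 + Cohort 2) versus PBO (Cohort 3") and names a t-test with equal variances. The section then adds 12 patients: "To account for attrition and a potential higher PBO rate, a total of 132 patients will be randomized", at 44 per group.

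SAP 3.4 gives the same SD, difference and N, but qualifies the power: "approximately 80% power, two-sided alpha of 0.05".

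On missing data, SAP 5.8 says "Missing evaluations will not be imputed". SAP 7 says of daily diary scores that "No imputation of the missing values will be made", and it sets a window of 14 days either side of calculated Day 29, so that "any Day 29 visit occurring outside that window will be excluded".

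**The concern.** This is the protocol's only quantitative justification for its size, and every input is printed, so a reader can check it. The check does not return 80%. Pooling two arms against one makes the comparison 80 versus 40, which is less efficient than 60 versus 60, and the result is nearer 78%. By the normal approximation, 80% needs 126 evaluable patients.

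The 12 added patients do not plainly close the gap. The protocol assigns them to attrition and a higher placebo response, yet about 6 of them are needed to reach the stated power. A patient with no usable Day 29 score contributes nothing to the t-test, because nothing is imputed. A reader could therefore take the trial as having 80% power with 12 patients in reserve, when the printed inputs support about half that reserve.

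**Working it through.** **Inputs.** Difference d = 1.6, SD s = 3, two-sided alpha 0.05 and N = 120 (Protocol 9.2); equal-variance t-test of pooled active versus placebo (Protocol 9.4.1.1); allocation 1:1:1, hence n1 = 80 and n2 = 40.

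**The plan's own figure, normal approximation.** The standard error is s × √(1/n1 + 1/n2) = 3 × √(1/80 + 1/40) = 3 × √0.0375 = 0.581. Then d/SE = 1.6/0.581 = 2.754, and power = Φ(2.754 − 1.960) = Φ(0.794) = 78.6%.

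**The same with the named test.** Noncentral t with 118 degrees of freedom, noncentrality 2.754 and critical value 1.980 gives 77.98%. The shortfall from 80% is 1.4 points by the normal approximation and 2.0 by the t-test.

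**Could another reading give 80%?** An equal split of 60 versus 60 gives 83.2% (normal) or 82.6% (t). A one-sided test at 80 versus 40 gives 86.6% or 86.3%. Neither lands on 80%, and the 2:1 two-sided reading is the one the text describes.

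**N needed for 80%.** By the normal approximation, n2 = 1.5 × (3 × (1.960 + 0.842)/1.6)² = 41.4, rounded up to 42, so 126 in total. Power at nearby sizes:

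| Evaluable | Active v placebo | Exact t | Normal |
|---|---|---|---|
| 120 | 80 v 40 | 78.0% | 78.6% |
| 126 | 84 v 42 | 79.96% | 80.6% |
| 127 | 85 v 42 | 80.1% | 80.7% |
| 129 | 86 v 43 | 80.9% | 81.5% |
| 132 | 88 v 44 | 81.8% | 82.3% |

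By the t-test, 80% is first reached at 127, or at 129 with three equal arms.

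**Rounding of the printed inputs.** The difference is printed to one decimal and the SD as a whole number. At 80 versus 40, by exact t:

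- With SD 3, power reaches 80% at a difference of 1.641, which prints as 1.6.
- With difference 1.6, power reaches 80% at an SD of 2.925, which prints as 3.
- With SD 3, differences from 1.55 to 1.65 give 75.4% to 80.4%.
- With difference 1.6, an SD of 2.9 gives 80.7%, so 0.1 on the SD moves power by 2.7 points.

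The printed precision therefore cannot separate 78% from 80%.

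**Loss from the 132 randomized.** The documents give no rate. Assuming loss falls in proportion on active and placebo, exact-t power is 81.8% at 0% loss, 80.6% at 3%, 79.8% at 5%, and 78.0% at 12/132 = 9.1%. It crosses 80% at 4.45%.

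**The case for a change.** The strongest case for a correction is that rounding works both ways. Values printing as 1.6 at SD 3 centre on 78%, not 80%, and a reader cannot recover an unrounded input that was never disclosed. The named test with the printed numbers misses the stated power, and none of the other readings tried gives 80% either. The SAP's precedence clause in Protocol 9.4 covers details of the analyses to be conducted, so it does not obviously override a design statement in Protocol 9.2. The correction would also take only one sentence.

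The arithmetic in this stands: on the printed values 80% is slightly high, and rounding shows only that 80% is possible. The argument about the 12 extra patients is weaker. Several rules limit how many patients drop out of the test:

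- Patients randomized but never dosed may be replaced (Protocol 4.1.3).
- Stopping study drug is not leaving the study (Protocol 7.1), and SAP 4 uses data up to withdrawal whatever the treatment duration.
- The rule against imputation in SAP 7 concerns missing daily scores. The visit score averages the available days of the preceding 7, so isolated missed entries do not remove a patient.
- The Day 29 analysis window of 14 days is far wider than the protocol's visit window of 1 day, so it keeps most off-schedule visits.

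Loss above 4.5% remains possible, but the documents do not establish it.

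**Conclusion.** No change is called for. On its printed inputs Protocol 9.2 overstates power at 120 evaluable patients by 1.4 to 2.0 points, and what remains is one missing qualifier that SAP 3.4 already supplies. The 132 planned exceeds the 127 to 129 that a strict 80% requires. Even if all 12 extra patients were lost, power would be 78%. A difference of that size, smaller than the effect of moving the assumed SD by 0.1, would not alter a phase 2a proof-of-principle decision or anything in the analysis.

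This rests on a difference of 1.6 and SD of 3 as printed, the 2:1 pooled comparison, and loss in proportion across arms. An analyst reporting the design can follow the SAP's wording. The 82% at 132 assumes full retention and should not be read as the expected power.
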